## 11.0 SPECIMEN COLLECTION AND BANKING (Not Applicable)

## 12.0 DATA MANAGEMENT

### *Analysis*

Aim 1. FLAIR, diffusion, T2\*/gradient, perfusion and volumetric scans will be reviewed by [name] for any new signal abnormality. Adverse events will be surveyed and summarized.

Aim 2. Retention (i.e., defined as completion of all study sessions) will be determined. Participants will also complete a survey regarding acceptability, including qualitative responses for treatment modification.

Exploratory Aim 3. Neurocognitive performance and affective symptoms/quality of life will be analyzed with repeated-measures mixed models.

Exploratory Aim 4. BrainHQ usage/retention, performance, and acceptability will be analyzed with repeated-measures mixed models.

**Power Considerations.** The aims of this study are to determine safety and feasibility. The retention rate of 80% was determined to ensure that recruitment in the planned follow-up studies would be feasible in the longer time span allowed by future grants. Although these results will not be as compelling in the absence of a sham control, these data will give us an estimate of the

potential effect sizes and response variability that we can anticipate in future randomized controlled trials.

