## 1.0 OBJECTIVES / SPECIFIC AIMS

The objective of this study is to establish the safety, feasibility, tolerability, and acceptability of high-dose accelerated intermittent theta burst (iTBS) repetitive transcranial magnetic stimulation (rTMS) to the left dorsolateral prefrontal cortex (dlPFC) in patients with amnestic Mild Cognitive Impairment (aMCI). We also seek to obtain preliminary efficacy data as well as feasibility / acceptability data of computerized cognitive training as an adjunct to iTBS rTMS. The long-term goal of this project is to obtain preliminary data to support future empirical studies of iTBS rTMS for aMCI, including future randomized controlled trials to devise the optimum rTMS therapeutic delivery (with variations in dosing parameters, cortical targeting, and MCI syndrome indications), with the ultimate goal of dementia prevention. *The scientific merit of this pilot study has been peer-reviewed and subsequently recommended for funding through the National Center of Neuromodulation for Rehabilitation (NC NM4R).*

**AIM 1: Establish the safety of an accelerated rTMS protocol for neurocognitive rehabilitation in aMCI.** We hypothesize that accelerated rTMS will be safe as indexed by 1) no clinically significant structural brain changes; 2) no decrements in neurocognitive function; 3) no significant adverse events.

**AIM 2: Establish the feasibility, tolerability, and acceptability of an accelerated rTMS protocol for neurocognitive rehabilitation in aMCI.** We hypothesize that 1) aMCI patients will consider the treatment acceptable and that 2) recruitment and retention will be feasible (> 80% retention).

**EXPLORATORY AIM: Establish the preliminary efficacy of an accelerated rTMS protocol for neurocognitive rehabilitation in aMCI.** We hypothesize that aMCI patients will demonstrate modest improvements on neurocognitive testing and self-reported affective symptoms and quality of life from pre- to post-treatment.

**EXPLORATORY AIM: Establish the feasibility, acceptability of computerized cognitive training as an adjunct to accelerated rTMS in MCI.** We hypothesize that aMCI patients will complete a range of exercises between sessions and at home (feasibility) and will rate the intervention as productive (acceptability).

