In this open-label, safety and feasibility trial, we will recruit 40 amnestic MCI (aMCI) patients (target completers N=30) through memory disorders and neuropsychology clinics, as overseen by PI and neuropsychologist [name]. We will recruit clinically well-defined participants who will meet stringent actuarial neuropsychological criteria for aMCI. **This study will employ identical procedures to an ongoing IRB-I approved NC NM4R pilot, *Neuromodulation and Plasticity in Cognitive Control Neurocircuitry in Chronic Stroke* (PI: [name]; Pro 83136).** Specifically, neuronavigation-based targeting of the left dorsolateral prefrontal node of the cognitive control network will be performed. This study will utilize accelerated rTMS using a MagVenture MagPro TMS System. All participants will receive treatment for eight, 3-min sessions of iTBS on each of three days within an eight-day span. Each session would be separated by 10 mins or more per participant comfort and convenience. To collect preliminary feasibility and acceptability data for a planned follow-up combinatorial intervention study, participants will complete computerized cognitive exercises in the intervening periods between same-day rTMS sessions. At pre- and post-treatment, participants will undergo brain MRI (FLAIR, diffusion, T2\*/gradient, volumetric scans, resting state) and computerized neurocognitive testing. As an open-label pilot study, there is no sham control group.

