## **4.0 STUDY ENDPOINTS**

### **AIM 1: Establish the safety of an accelerated rTMS protocol for neurocognitive rehabilitation in aMCI.**

Primary Outcomes: Clinically significant structural brain changes; Neurocognitive performance changes; Adverse events

Secondary Outcomes: Psychopathology symptom changes

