**Sessions 3-5: rTMS (2 – 3 hours).** A MagVenture MagPro TMS System will be utilized. All participants will receive open-label treatment for approximately eight, 3-minute sessions of intermittent theta burst rTMS on each of three days within an eight-day span. A single session=600 pulses at 120% rMT, iTBS triplets at 50 Hz for 2 s and repeated every 10 s for a total of 190 s to left dlPFC. Total pulses=14,400. To enable adherence and retention, the days do not need to be contiguous. Same day sessions will be separated by 10-15 minutes, but more accounting for participant comfort. After each day of treatment, participants will be asked to complete an rTMS acceptability questionnaire. During treatment breaks participants will complete Momentary Assessment of TMS and 10-15 minutes of Brain HQ exercises between each session and will also have the option of completing tasks at home on intervening days during the treatment schedule. At the end of the final treatment session, participants will be asked to rate the exercises based on difficulty and enjoyment.

**Session 6: In-person Post-treatment Neurocognitive/Neuropsychiatric Assessment (2 - 3 hours).** Within one week following treatment, participants will repeat the pre-treatment neuropsychiatric and neurocognitive assessment for assessment of pre/post treatment changes.

**Session 7: Post-treatment MRI Scans (1 - 2 hours).** Within one week following treatment, participants will repeat the pre-treatment MRI scans for assessment of pre/post treatment changes.

**Session 8: 1 – 3 weeks post-treatment completion.** During the intervening weeks after Sessions 6/7 and before Session 9, the participants will be asked to remotely complete surveys using REDCap. Participants will also be provided with a research account for BrainHQ and asked to engage in at least 20 minutes of brain exercises daily until Session 9.

**Session 9: 4 weeks post-treatment completion.** Participants will again be asked to complete surveys using REDCap. Participants will also be asked to complete the MoCA remotely, as well as acceptability/satisfaction questionnaires regarding the rTMS and BrainHQ interventions.

**Participant Compensation.** Participants will be compensated as follows:

Consent & Session 1:	\$40 for screening and pre-treatment assessments
Session 2:	\$50 for the pre-treatment MRI
Sessions 3 to 5:	\$120 for rTMS treatment (i.e. \$40/day)
Sessions 6 and 7:	\$100 for post-treatment assessments and MRI

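### Neurocognitive change is an Aim 1 primary safety outcome, but the Aim 1 analysis omits it and nothing says what would count as a decline

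*Combined protocol and SAP*

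**What the plan says.** Section 1.0 says that safety under Aim 1 will be judged by three indices, the second of which reads "2) no decrements in neurocognitive function". Section 4.0 gives the matching outcomes: "Primary Outcomes: Clinically significant structural brain changes; Neurocognitive performance changes; Adverse events".

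The Aim 1 paragraph in section 12.0 (Analysis) has two sentences. The first has the scans reviewed for new signal abnormality. The second is "Adverse events will be surveyed and summarized". Neurocognition is not mentioned. The scores appear under Exploratory Aim 3: "Neurocognitive performance and affective symptoms/quality of life will be analyzed with repeated-measures mixed models". The hypothesis for that aim in section 1.0 is that "aMCI patients will demonstrate modest improvements on neurocognitive testing".

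On design, section 2.0 states "As an open-label pilot study, there is no sham control group". Section 10.0 (Session 6) sets the retest: "Within one week following treatment, participants will repeat the pre-treatment neuropsychiatric and neurocognitive assessment". Between the two assessments, participants do BrainHQ training on treatment days. Section 15.0, on potential changes in cognitive function, says that batteries before and after treatment will look for such changes. It gives no score, threshold or decision rule.

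**The concern.** One of three primary safety conclusions has no stated route from data to conclusion, in a population defined by memory impairment. Whoever reports Aim 1 would have to choose the test, the size of decline, and the level (group or individual) after seeing the results.

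The analysis that does exist is also poorly suited to the safety question. Its terms are not given, but the natural reading is mean change over time. Without a control arm, that mean combines any effect of stimulation with practice on a repeated battery and with gain from training. A mean that is flat or slightly up is what one would see with no harm, and also with a modest harm offset by practice. A mean can also dilute a decline confined to a few participants.

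**Working it through.** **Text check.** Each Aim 1 primary outcome in section 4.0 against the Aim 1 analysis in section 12.0:

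- Structural brain change: scan review for new signal abnormality.
- Adverse events: surveyed and summarized.
- Neurocognitive performance change: nothing under Aim 1; a mixed model under Exploratory Aim 3.

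Other places that might supply a criterion do not. The 16th-percentile cut-off in section 5.0 is for eligibility. In section 13.0, quality control verifies assessment scores, adverse events may be identified from visit assessments, and the DSMB sees unnamed variables that may indicate harm. The weekly physician contact in section 15.0 covers mood, functioning and safety. The withdrawal reasons in section 14.0 do not name cognitive decline. None sets a score rule.

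**Training between the assessments.** Section 3.0 gives 20 minutes per treatment day, 60 minutes over three days. Section 10.0 gives "10-15 minutes of Brain HQ exercises between each session". Eight sessions leave seven gaps, so 7 × 10 to 7 × 15 = 70 to 105 minutes per day. The two statements must be reconciled. Either way, training precedes the retest. The one later cognitive test, the MoCA at 4 weeks, is a single score taken remotely. It follows up to 28 paid home sessions ($126 / $4.50), or 28 × 20 = 560 minutes, so it does not remove the problem.

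**What a zero mean change would exclude (illustration).** The plan states no figure to reproduce. Inputs: n = 30 completers or 40 enrolled (section 6.0); test-retest correlation r = 0.6, 0.7, 0.8 (assumed); equal SD at both visits; one score, paired comparison.

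SD of change = √(2(1 − r)) = 0.894, 0.775, 0.632 baseline SD.

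95% CI half-width = t × SD of change / √n:

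- n = 30: 0.334, 0.289, 0.236 SD
- n = 40: 0.286, 0.248, 0.202 SD

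If practice and training add a gain G, the observed mean estimates G minus the decline. An observed zero is then compatible with declines up to G plus the half-width. The documents give no size for G. With an assumed G of 0.1 SD and n = 30, the limit is 0.34 to 0.43 SD; with 0.2 SD, it is 0.44 to 0.53 SD.

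**What an individual rule would show (illustration).** Take a reliable-change cut-off of 1.645 × SD of change, which is 1.47, 1.27 or 1.04 SD for the three correlations. With no true change:

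- Expected flags per score: 30 × 0.05 = 1.5.
- Chance of at least one flag: 1 − 0.95^30 = 79%.
- Flagged on at least one of five independent scores: 30 × (1 − 0.95^5) = 6.8 of 30.
- If 0 of 30 are flagged, the exact two-sided 95% upper limit is 1 − 0.025^(1/30) = 11.6%. This bounds the flag rate, not the rate of true decline.

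The exact lower limit first exceeds 5% at 5 of 30 (5.6%). Comparing that with a two-sided 5% paired test of the mean, with no practice gain left in the scores:

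- Uniform 0.3 SD decline: at least five flags with probability 15 to 29%; power for the mean 43 to 71%.
- Decline of an assumed 1.5 SD in 5 of 30 participants (mean 0.25 SD): at least five flags with probability 32 to 65%; power for the mean 20 to 30%.

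The two summaries answer different questions, so the count supplements the mean and does not replace it.

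**The case against.** The strongest reply is that this is largely a missing cross-reference. Section 4.0 lists the same neurocognitive outcome under both aims, and a mixed model estimates change in either direction, so a mean decline would appear in the Aim 3 output. Section 15.0 ties the batteries to cognitive safety. Overt individual decline can be recorded as an adverse event, and there is weekly physician contact and a DSMB. Section 12.0 itself concedes that results are less compelling without a sham arm. This is a pilot with no power claim.

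Much of that stands, and it rules out some stronger readings. A reader might infer that cognitive harm would go unseen; the documents do not support this, because the scores are collected and modelled and adverse-event capture is broad. A reader might also infer that the plan intends to treat a non-significant mean as proof of safety; no section says so. Nor is absence of a decrement itself the listed endpoint: it is the hypothesis in section 1.0, while the endpoint in section 4.0 is performance change.

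What does not stand is that these provisions fill the gap. Sections 1.0 and 4.0 list neurocognition separately from adverse events, and a cross-reference alone would still leave no statement of what the safety conclusion rests on.

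It is also fair that an interval-limited conclusion sets no margin in advance. The documents give no basis for one, and for a pilot, reporting what the interval excludes is adequate. If the investigators have a margin in mind, they can state it beforehand.

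**Conclusion.** The concern holds and should be fixed. Followed as written, section 12.0 leaves a primary safety outcome out of the Aim 1 analysis, and no criterion for a decline is given elsewhere. This rests on the text alone.

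The size is illustrative. It depends on an assumed retest correlation of 0.6 to 0.8, one score and 30 completers: a zero observed change excludes only mean declines larger than 0.24 to 0.33 SD, and less is excluded if there is practice or training gain. The figures show how weak the inference from a flat mean would be; they do not measure a flaw in a stated power calculation, since there is none.

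**What to change.** Add to Aim 1 in section 12.0:

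1. **Main analysis.** For one or a few pre-named scores, report mean change with its 95% CI from the mixed model already planned. Limit the safety conclusion to the size of decline that the interval excludes. State that practice and training gain cannot be separated from the effect of stimulation.
2. **Supplement.** Report the number of participants who decline beyond a pre-stated reliable-change cut-off, with an exact 95% CI. Set it beside the chance expectation: about 1.5 of 30 per score at a one-sided 5% cut-off, and about 6.8 of 30 on at least one of five independent scores. State beforehand whether counting is per score or across scores. Adjust for practice if a suitable published retest source is named; such norms would not remove BrainHQ gain.
3. **Missing scores.** Report how many participants have no post-treatment score and why, including withdrawal for adverse events, since that loss may be related to harm.

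Separately, reconcile the on-site BrainHQ times in sections 3.0 and 10.0.

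The cost is a paragraph of text and a small extra analysis of scores already collected. The downside is a more modest safety statement and, if practice adjustment is used, reliance on an external source.

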### **13.0 PROVISIONS TO MONITOR THE DATA TO ENSURE THE SAFETY OF SUBJECTS**

The PI will be responsible for the overall monitoring of the data and safety of study participants. The PI's plan for ensuring safety and data integrity follows.

**Quality Control.** QC will include regular data verification at weekly meetings with the PI, Co-Is and study personnel. This will include verification of the documentation (Integrity of the Consent and HIPPA, scores on the assessments, MRI scanning information), study progress and participant status, any adverse events, and any protocol deviations. Events determined by the PI to be unanticipated problems involving risks to subjects or others (UPIRTSOs) will be reported by the PI to the IRB as soon as possible and no more than 10 working days per policy.

**Safety Training.** Before any investigator or assistant is allowed to enter the scanner room, they are required to take an extensive MRI safety course (with annual refresher courses) that cover powering down (or quenching) the magnet for patient safety and with established procedures for expediting participant contact with emergency medical personnel, should the need arise. These courses are run by the MUSC Center for Biomedical Imaging and are a prerequisite for obtaining privileges to book and use scanner time. Prior to administering TMS all personnel must be trained and certified by Drs. [name] (Co-I) and [name] (Co-I).

#### **Medical Emergencies:**

1. Emergency responding in the scanner is facilitated by having two research staff running a scan. In the event of an emergency, one of these individuals remains with the participant and undocks the scanner bed from the magnet bore. This bed can easily be wheeled out of the scan room to facilitate speedy access to arriving emergency medical personnel. The second researcher calls 9-1-1 from the scanner suite and gives details of the participant's level of medical distress and location. Next, this person goes out to the front of the scanner building to flag down arriving emergency personnel and to direct them to the participant.
2. Drs. [name] and [name] are licensed physicians and will be on call during all sessions and rTMS sessions (or a similarly trained physician) to respond to any subtler potential medical situations.
3. These guidelines are in full agreement with the Center for Biomedical Imaging safety protocols and with published guidelines by a panel of experts in conducting TMS/rTMS and TMS/neuroimaging work for both research and clinical purposes (Rossi et al., 2009).

**Suicidal Intent.** Participants who have made a suicide attempt in the past year will be excluded. Also, suicidal intent will be assessed at the initial assessment phase of the study (during MINI Depression module) and with the Columbia Suicide Severity Rating Scale-Screen Version with Triage Points. At the initial assessment, the "Lifetime/Recent" version will be used. Consistent with the triage points determined by the scale authors, any positive endorsement to items 3 – 6 will necessitate immediate consultation with the PI. Any positive endorsement of items 4 – 6 and

participation will be discontinued. Depending upon the follow-up to endorsement of item 3 (passive ideation), participation may also be discontinued. Any participant endorsing these items will be referred to immediate consultation with the PI and provided appropriate referrals and follow-up contact to ensure engagement in care. For imminent suicidal intent, an emergency outpatient appointment or an in-house psychiatric consult will be arranged. MUSC police will be called directly in the event that the clinician deems the participant to be imminently of risk of harming him/herself and refuses to cooperate with a plan to report to the emergency psychiatric consult.

**Ethical Research Practices.** Ethical guidelines for clinical research will be followed strictly and all information obtained in the study will be kept strictly confidential. Data will be assigned coded identifiers and all names will be removed from study assessment and outcome data. Files linking participant names or identifying information to the coded identifier will be stored in a password-protected file, on a password protected desktop computer in a locked laboratory. Demographic and other identifying information will be stored separately from consent forms to eliminate the possibility of participant identification; signed consent forms will be locked in secure cabinets separate from data files. The files linking names to IDs will be deleted at the conclusion of the research project. De-identified data will be stored indefinitely following the conclusion of the project. Only the PI and active research staff will have access to the de-identified data. The PI and all research staff and mentors will be responsible for and will comply with mandated reporting rules. All researchers will be obligated to demonstrate that they have remained abreast of all guidelines and rules related to the Health Insurance Portability and Accountability Act (HIPAA). Each member of the research staff will complete focused training on each task for which they are responsible and will perform ongoing quality control for others performing similar work. The PI and/or study coordinator will produce quarterly administrative reports describing study progress including accrual, demographics, and participants' status. Reports will describe adherence to inclusion/exclusion criteria and the study protocol in addition to any unanticipated problems in the category of risks to participants or others as well as any adverse events. All collected data will be obtained for research (and participant safety) purposes only.

**Confidentiality.** Any discussion of identifying sensitive and information will occur in private rooms at MUSC. Regarding documentation, participants' names will appear only on the IRB-approved Consent, HIPAA, and payment forms, initial screening form, and in a separate key file that links individual participant names and contact information to a random participant identification code. The participant identification code will be assigned to the individual during Visit 1 and all subsequent data collection will reference this code. The key linking individual identifying information to the participation code will be maintained in an electronic database accessible only to the PI and their designees in a password-protected file on an encrypted and password protected network (MUSC LAN). The questionnaire data collected through REDCap will be referenced by participant ID only and collected via a HIPAA compliant interface and downloaded to the MUSC server once a participant has completed participation. If a participant consents to participate at the interview, the initial screening form will be entered into a secure electronic database according to the assigned participation code and then locked a secure office, separate from payment and consent forms including health information. If a participant declines consent or is lost to follow-up (i.e., defined as not appearing for intake within 1 month of screen), the screening form will be securely shredded. The consent, HIPAA, and payment forms will be kept in a locked cabinet in a locked office. All other collected paper (e.g., interview responses) and electronic (e.g., questionnaire, neurocognitive, MRI data) files, including audio recording files, will be identifiable

only by participant code and stored in locked file cabinets or on the secure MUSC LAN at the Institute of Psychiatry (non-MRI data) and Center for Biomedical Imaging (MRI data). The key file linking names to IDs will be deleted after data collection is complete.

Consent and HIPAA forms will be kept on file for 6 years. Contact information is kept on file for 6 years if the participant consents to allowing their information to remain active in our files, or the contact information is destroyed immediately after the study is completed if participants chose that option on the consent form. Although individual-subject analyses may be written up in publications, the individual subjects producing that data will never be identified by name or initials, or any other identifying information.

*Other protections against risk.* In designing this trial, the research team sought to maximize data collection within the overall priority of maintaining participant comfort and safety. As was discovered in the pilot study by George and colleagues, the proposed design is feasible, does not impose unreasonable expectations of time or effort, or expose patients to risks or limit them from the best available care. In the very unlikely event that a subject endorses transient alcohol or substance abuse during the course of this study, the coordinator will confer with a physician co-investigator prior to proceeding with any treatment.

*Adverse Events & Trial Safety.* Potential conflicts of interest will be reported using the NIH rules for disclosure. Adverse Events (AEs)/Serious Adverse Events (SAEs) occurring during the course of the project will be collected, documented, and reported in accordance with protocol and IRB reporting requirements. All research staff involved with adverse event reporting will receive general and protocol specific AE/SAE training including identification, assessment and evaluation, and documentation and reporting. Any potential adverse events will be identified during the course of the study from participant self-report and administration of the visit assessments and procedures. Research staff will identify adverse events and obtain all available information to assess severity, seriousness, study relatedness, expectedness, outcome and the need for change or discontinuation in the study intervention.

An Adverse Event (AE) is defined as any unwanted change, physically, psychologically or behaviorally, that occurs in a study participant during the course of the trial is an adverse event. A Serious Adverse Event (SAE) is defined as an adverse event that has one of the following outcomes:

- Results in death,
- Is life-threatening,
- Requires inpatient hospitalization or prolongation of existing hospitalization,
- Results in persistent or significant disability/incapacity, OR
- Requires intervention to prevent one of the above outcomes.

Adverse events are generally documented on AE Logs and AE Case Report Forms (CRFs). Additional relevant AE information if available should be documented in a progress note in the research record as appropriate to allow monitoring and evaluating of the AE.

When a reportable SAE is identified, the research staff will notify the MUSC Institutional Review Board (IRB) and DSMB within 24 hours and complete the AE report form in conjunction with the PI. The MUSC IRB meets monthly and is located at [name]. Communication with the IRB is through email, memos, official IRB forms, and online reporting.

If complete information is not available when the initial 24-hour SAE report is disseminated, follow-up information will be gathered to enable a complete assessment and outcome of the event. This information may include hospital discharge records, autopsy reports, clinic records, etc. The research staff will attach copies of source documents to the SAE report for review by the PI.

We will report adverse events to the Medical University of South Carolina (MUSC) Institutional Review Board (IRB) as soon as possible, but no later than 10 working days after the investigator first learns of the event. The MUSC IRB AE reporting requirements are as follows: All deaths that occur during the study or 30 days post termination from the study are required to be reported as adverse events even if they are expected or unrelated. Other adverse events are reportable to the MUSC IRB if the AE is 1) unexpected AND 2) related or possibly related AND 3) serious or more prevalent than expected. All three criteria must be met for an AE to be reported to the MUSC IRB. The IRB definition of unexpected is that the AE is not identified in nature, severity or frequency in the current protocol, informed consent, investigator brochure or with other current risk information. The definition of related is that there is a reasonable possibility that the adverse event may have been caused by the drug, device or intervention. Reportable AEs are reviewed by the IRB Chair and reported to the IRB Board at the next meeting.

The potential risks and benefits and methods to minimize these risks are outlined above. The research staff will report any unexpected AEs or any scores of "severe" on the side-effect symptom rating form or any FDA-defined serious AEs to the PI within 24 hours so that the PI can decide on the appropriate action. All unexpected AEs will be monitored while they are active to determine if treatment is needed. Study procedures will follow the FDA's Good Clinical Practice Guidelines ([www.fda.gov/oc/gcp](http://www.fda.gov/oc/gcp)).

